1.1. Background and rationale

Preterm and small for gestational age (SGA) infants have a 2- to 10-fold higher risk of mortality than infants born at term and with normal birth weight, and are particularly vulnerable to infection, malabsorption, necrotizing enterocolitis, difficulty feeding, and growth failure. Numerous trials conducted in the last ten years have reported that probiotics can improve short- and long-term mortality, necrotizing enterocolitis and sepsis rates, and growth and neurodevelopment in preterm and low birth weight infants. However, most trials have been small and with high to moderate risk of bias. There have been no trials in SGA infants. The World Health Organization (WHO) guideline development group (GDG) and other organizations have recommended that further large high-quality trials are implemented to provide evidence of sufficient quality and applicability to inform policy and practice.

This large, multi-country trial will address this recommendation, by providing robust evidence on the effects of probiotic supplementation on mortality, morbidity, and growth in preterm or term SGA infants in the first 6 months of life in five countries in South Asia and Sub-Saharan Africa. Results from this trial will help inform policy and practice for probiotic supplementation in preterm and SGA infants, improve the certainty of evidence on critical outcomes and strengthen the understanding of optimal strains, dosing and duration of probiotic supplementation and related impact in high burden LMICs.

1.2. Objectives

The primary objectives are:

- For preterm infants, to assess the effectiveness of probiotic supplementation on mortality from enrolment to 6 months of age.
- For term SGA infants, to assess the effectiveness of probiotic supplementation on underweight-free survival from enrolment to 6 months of age.

The secondary objectives are, among preterm and term SGA infants:

- To assess safety of probiotic supplementation from enrolment to 6 months of age, assessed as:
 - Episodes of serious adverse events (SAEs)
 - Episodes of sepsis due to the probiotic strains *B. infantis* or *L. rhamnosus*.
- To assess the effect of probiotic supplementation on the following outcomes at hospital discharge, 1 month and 6 months of age:

- All cause mortality (for the 6 month endpoint, this will be evaluated as a secondary outcome for term SGA infants, and as a primary outcome for preterm infants)
- Cause specific mortality due to necrotising enterocolitis, sepsis, severe diarrhoea
- Episodes of necrotising enterocolitis, sepsis, severe diarrhoea
- Episodes of pathogen specific sepsis (including Streptococcus, Staphylococcus, Klebsiella, Escherichia coli, Acinetobacter spp) including their serotypes and genotypic sequences
- Episodes of hospitalisation
- To assess the effect of probiotic supplementation on the prevalence of wasting, underweight, and mean weight for age z score (WAZ) and weight for length (WLZ) scores at 6 months of age
- To assess the effect of probiotic supplementation on the abundance of *B. infantis* and *L. rhamnosus* and other bacteria in infant faecal specimens at enrolment, 7 days, 28 days and 6 months of age; and in maternal faecal specimens at enrolment, including their serotypes and genotypic sequences.
- To assess the effects of probiotic supplementation on the primary outcome in the following subgroups:
 - o prematurity (<32weeks, 32-<37weeks), among preterm infants only
 - birth weight (< 1.5kg, 1.5 to < 2.5kg, 2.5+ kg)
 - o preterm and SGA status (preterm SGA, preterm AGA), among preterm infants only
 - o vaccination (fully, partially, not vaccinated) from enrolment to 6 months of age
 - feeding type (exclusive, predominant, partial) at 1 month, 3 months, 6 months of age
 - early initiation of enteral feeding (including mother's milk, donor milk, infant formula)
 (within < 1hour, 2-< 24hour, 24+ hours after birth)
 - micronutrient supplement intake (multiple micronutrients, iron, vitamin A, vitamin D, zinc) from enrolment to 6 months of age
 - o receipt of antibiotics from enrolment to 6 months of age

2. Study methods

2.1. Trial design

This is a multi-country, individually-randomised, double-blinded, parallel-group placebo-controlled superiority trial implemented among preterm and term SGA infants in five countries: Bangladesh, Pakistan, Ethiopia, Nigeria, Kenya.

2.2. Randomisation and blinding

Infants will be randomized in a 1:1 ratio to receive either intervention (*B. infantis* and *L. rhamnosus*) or control (placebo for *B. infantis* and *L. rhamnosus*) once daily for a period of 28 days. Randomisation will be stratified by site and by infant status (i.e. preterm, or term SGA), so that for each site there will be two randomisation lists, one for preterm infants and one for term SGA infants.

A statistician who is otherwise uninvolved with the study will generate the randomisation lists for each site using randomly permuted block sizes. This randomisation list will be embedded within the data

collection system. At the time of enrolment, a participant will be allocated to the next trial arm allocation on the randomisation list for their stratum.

Participants (i.e. infants and their care providers), hospital staff and all investigators (i.e. the site teams including the intervention, data collection, data management and data analysis teams, and the WHO team including the project managers and internal statistics team) will be blinded to the group allocation.

The intervention powder will be identical in appearance, consistency, taste and smell to the placebo powder. The intervention and placebo will be placed in foil sachets that are also identical in appearance and packaging. The sachets will be labelled, assembled into boxes and packs by an experienced packing team. The packing team will ensure that all labelling does not distinguish between placebo and intervention groups.

2.3. Sample size

The primary outcome for preterm infants is mortality at 6 months, which is assumed to be 10% in the control arm. A total of 8,602 preterm infants with data on this outcome would be needed for 90% power to detect a 20% relative reduction in mortality risk at 6 months in the intervention arm (i.e. 8% versus 10%), with 5% significance level. The 9,500 preterm infants expected to be enrolled across the 5 sites will allow 9% loss to follow up in determining the primary endpoint among preterm infants for a total of 9,453 preterm infants enrolled.

The primary outcome for term SGA infants is underweight free survival at 6 months, which is assumed to be 23% in the control arm. A total of 3,750 term SGA infants with data on this outcome would be needed for 90% power to detect a 20% relative improvement in underweight free survival in the intervention arm (i.e. 27.6% versus 23%), at 5% significance level. The 4,500 term SGA infants expected to be enrolled across the 5 sites will allow 16% loss to follow up in determining the primary endpoint among term SGA infants for a total of 4,465 term SGA infants enrolled.

2.4. Statistical interim analyses and stopping guidance

An independent Data Safety and Monitoring Board (DSMB) will review periodic data on trial progress and safety. No formal stopping rules relating to safety are planned, but the DSMB will be able to act on safety concerns at any point without alpha spending. Regarding efficacy, a formal interim efficacy analysis of primary outcome data will be done when 40-50% of trial participants have data available on the primary outcome (in each group, i.e. preterm and term SGA). The interim efficacy analysis will be governed by the Haybittle-Peto rule. An external statistician who is otherwise uninvolved in the trial will summarise primary outcome data by trial arm (A or B) but the DSMB will not know whether A or B are the intervention or control arms. These data will be discussed at a closed session DSMB meeting attended only by the DSMB members and the external statistician. The effect of the intervention on the primary outcome at this time point will be evaluated using the methods described in section 5.3. If there is strong evidence of a difference (p<0.001) in primary outcome between trial arms, then the trial arm will be unmasked to the DSMB who will then have the power to request that the trial be stopped or altered. Following the Haybittle-Peto rule, no adjustment to the significance level used in the final analysis will be made. These plans will be finalised by the DSMB at their first meeting and reflected in the DSMB charter.

Other than the formal interim efficacy analysis described above, no formal stopping rules relating to either efficacy or safety data are planned, with any recommendations from the DSMB to continue or discontinue to be guided by the balance of risks and benefits alongside other considerations such as

external new information. These aspects will be considered for the preterm and term SGA infant groups independently.

2.5. Timing of final analysis

Analysis for all outcomes will be done when all infants have completed the six-month visit (or have been censored before this visit), when all trial data have been cleaned, finalized and the database locked.

2.6. Timing of and sources for outcome assessments

Timing of, and sources for, primary outcome assessment

- The primary outcome in preterm infants, mortality from enrolment to 6 months of age, will be assessed based on SAE data capture during this period. Safety data, including on SAEs, will be actively solicited, daily from enrolment to 7 days post the last supplement dose, and then at 4-weekly visits. This will be supplemented by passive surveillance where all research staff, monitoring staff and health facility staff will be asked to report any SAE in a study participant that they become aware of.
- The primary outcome in term SGA infants, underweight-free survival from enrolment to 6 months
 of age will be assessed based on continuous SAE data capture (as described above) during this
 period, in combination with anthropometric data collected at the month 6 visit.

Timing of, and sources for, secondary outcome assessment

- Safety based on episodes of SAEs will be assessed based on continuous SAE data capture from enrolment to 6 months of age.
- Safety based on episodes of sepsis due to the probiotic strains *B. infantis* or *L. rhamnosus* will be assessed based on continuous SAE data capture from enrolment to 6 months of age.
- All cause and cause-specific mortality due to necrotising enterocolitis, sepsis, severe diarrhoea; episodes of necrotising enterocolitis, sepsis, severe diarrhoea; episodes of pathogen specific sepsis; and episodes of hospitalisation will be assessed based on continuous SAE data capture, supplemented by laboratory results from enrolment to 6 months of age. These data will be evaluated at three time points: at hospital discharge (on the basis of hospitalisation data), at age one month, and at age six months.
- Prevalence of wasting, underweight and mean WAZ and WLZ scores at 6 months of age will be assessed based on anthropometric data collected at the month 6 visit.
- Abundance of *B. infantis* and *L. rhamnosus* and other bacteria will be evaluated in laboratory tests done on infant faecal specimens at enrolment, 7 days, 28 days and 6 months of age; and in laboratory tests done on maternal faecal specimens at enrolment.

3. Statistical principles

3.1. Confidence intervals and p-values

All applicable statistical tests will be two-sided and 95% confidence intervals will be presented.

3.2. Adherence and protocol deviations

Compliance to the protocol schedule will be assessed based on the percent of participants who have attended the scheduled visits within the permitted time windows.

3.3. Analysis populations

The primary analysis populations will be:

- All randomised preterm infants (Preterm ITT)
- All randomised term SGA infants (Term SGA ITT)

For primary outcome 1 (mortality in preterm infants), all randomised preterm infants will be the analysis population.

For primary outcome 2 (underweight free survival in term SGA infants), all randomised term SGA infants will be the analysis population.

For all secondary outcomes, analyses will be conducted and presented separately for the two analysis populations.

The primary analysis will be done by intention to treat (ITT), i.e. participants will be included according to the trial arm they were randomised to, regardless of whether interventions were received. The only exception to this will be if the participant's mother withdraws their consent for their data to be used.

Missing data will be handled using complete case analysis as the primary approach. Multiple imputation methods may also be used as a sensitivity analysis if substantial missing data exist (>10% missing).

"Per-protocol" secondary analyses will also be conducted, among the following populations, with participants analysed according to the treatment received rather than the treatment to which they were randomised (if the two differ):

- Randomised preterm infants who receive all 28 days of intervention/control (Preterm PP): for primary outcome 1 and all secondary outcomes
- Randomised term SGA infants who receive all 28 days of intervention/control (Term SGA PP): for primary outcome 2 and all secondary outcomes

4. Trial population

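### The SAP plans no estimate of probiotic-strain sepsis over all exposed infants, and its ratio models give none if an arm has no cases

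*SAP*

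**What the plan says.** Section 1.2 opens the secondary objectives with "The secondary objectives are, among preterm and term SGA infants". The first of them is "To assess safety of probiotic supplementation from enrolment to 6 months of age, assessed as" two things: serious adverse events, and "Episodes of sepsis due to the probiotic strains" contained in the product. Safety is therefore a secondary objective that names both groups together.

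Section 3.3 then sets the rule for how such outcomes are analysed: "For all secondary outcomes, analyses will be conducted and presented separately for the two analysis populations". Each ITT and per-protocol population listed there is either preterm or term SGA. No combined population and no safety population is defined. Where section 5.3 asks for overall figures as well as figures by arm, the natural reading is both arms together within one population, not both infant groups together.

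Section 2.2 describes one product given once daily for 28 days, 1:1 allocation, and separate randomisation lists by site and by infant status.

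Section 5.2 gives strain sepsis a case definition (suspected sepsis with a probiotic strain grown from blood) but does not say whether it is summarised as a proportion or a rate. For comparisons between arms, section 5.3 offers a log-link binomial model or modified Poisson for risks, and a random-effects Poisson model for rates.

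**The concern.** Analysing efficacy separately follows from the design, because the two groups have different primary outcomes and their own sample sizes. That reason does not carry over to a product-specific harm that may be very rare. Both groups receive the same product for the same period under the same surveillance plan (section 2.6). Because allocation is 1:1 within site and infant status, a combined comparison stratified by both factors keeps the randomised comparison intact.

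Two things are at stake. First, the final report could hold two separate statements about this harm, each with a fairly wide limit, and no prespecified figure for all infants who received the product. Second, it could lack a usable interval altogether. If one arm has no cases, the estimated log ratio is infinite; if both arms have none, the ratio is undefined. Section 5.3 gives a fallback for convergence failure of the binomial model, but modified Poisson estimates the same ratio and has the same problem.

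**Working it through.** **Inputs.** Section 2.3 gives "The 9,500 preterm infants expected to be enrolled across the 5 sites" and "The 4,500 term SGA infants expected to be enrolled across the 5 sites". With 1:1 allocation (section 2.2), the intervention arm has about 9,500/2 = 4,750 preterm and 4,500/2 = 2,250 term SGA infants, 7,000 in all. Section 3.1 asks for two-sided tests and 95% confidence intervals. The SAP gives no expected rate of strain sepsis, so the case counts below are assumptions.

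**The plan's own figures.** The SAP states no precision for the safety outcomes. Its sample sizes do reproduce, using n per arm = [1.96·√(2·p̄·(1−p̄)) + 1.2816·√(p₁(1−p₁) + p₂(1−p₂))]² / (p₁−p₂)²:

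- 10% versus 8%: 4,301 per arm, 8,602 in total; 8,602/0.91 = 9,453.
- 23% versus 27.6%: 1,875 per arm, 3,750 in total; 3,750/0.84 = 4,465, rounded up.

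**Upper limit on risk.** With zero cases, the exact (Clopper-Pearson) two-sided 95% upper limit is 1 − 0.025^(1/n):

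- preterm: 1 − 0.025^(1/4,750) = 0.78 per 1,000
- term SGA: 1 − 0.025^(1/2,250) = 1.64 per 1,000
- combined: 1 − 0.025^(1/7,000) = 0.53 per 1,000

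With e cases, the limit is the 97.5% point of a beta distribution with parameters e+1 and n−e. The table puts the same number of cases in each denominator; limits are per 1,000.

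| Cases | Preterm | Term SGA | Combined |
|---|---|---|---|
| 0 | 0.78 | 1.64 | 0.53 |
| 1 | 1.17 | 2.47 | 0.80 |
| 2 | 1.52 | 3.21 | 1.03 |
| 3 | 1.85 | 3.89 | 1.25 |

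With zero cases, the combined limit is about 32% below the preterm limit (5.27 against 7.76 per 10,000) and about 68% below the term SGA limit (5.27 against 16.38). If only the evaluable numbers from the sample-size section count (4,301, 1,875 and 6,176), the zero-case limits are 0.86, 1.97 and 0.60 per 1,000.

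**What the combined limit means.** It refers to the average risk over a mix of 4,750/7,000 = 68% preterm and 32% term SGA infants. It remains valid for that average when risks differ, because the probability of no case, ∏(1−pᵢ), is never larger than (1−p̄)ⁿ. It does not bound each group's own risk. For example, a preterm risk of 0.70 per 1,000 with no risk in term SGA infants averages 4,750 × 0.70/7,000 = 0.475 per 1,000. That is below the combined limit of 0.53, although the preterm risk itself is above it.

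**Chance of observing a case.** At an assumed true risk r, this is 1 − (1−r)ⁿ.

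| Assumed risk per 1,000 | Preterm alone | Term SGA alone | All intervention infants |
|---|---|---|---|
| 0.1 | 38% | 20% | 50% |
| 0.2 | 61% | 36% | 75% |
| 0.5 | 91% | 68% | 97% |
| 1.0 | 99% | 90% | 99.9% |

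The last column is not a gain from pooling. At 0.2 per 1,000, the chance of a case in at least one of the two groups is 1 − 0.387 × 0.638 = 0.753, the same 75%. Reporting both groups, as the SAP already plans, shows the same cases.

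**The case against.** The strongest reply is that the split is a consistent design choice. Randomisation lists, primary objectives, sample sizes, analysis populations and flow diagrams are all separate, and section 2.4 has the monitoring board weigh the groups independently. A joint heading over the secondary objectives does not oblige the sponsor to pool. This stands as far as it goes: the SAP does not contradict itself, and the separate results should stay, since risk may differ by group. But the rule for stopping considerations does not bar a combined estimate in the final analysis.

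Several stronger readings are tempting but not supported:

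- **That information is discarded.** Counts by arm will be reported for each group, and a reader can add them. What a reader cannot rebuild from split tables is a comparison stratified by site and status, and a sum made after the results are known is less credible than a planned estimate.
- **That pooling makes the harm easier to detect.** The calculation above shows that it does not change the chance of seeing a case.
- **That the combined limit is simply the better one for each group.** It is an average over the enrolment mix. If risk is concentrated in preterm infants, their own limit remains the relevant one.
- **That the same argument covers serious adverse events.** These include deaths and hospital admissions, and preterm control mortality alone is assumed to be 10%, so rarity gives no reason to pool them.

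Two reservations remain. The clinical sepsis definitions are in a protocol annex that is not shown, and the SAP does not document whether blood is cultured equally often in the two groups. The protocol might also plan a combined safety analysis; the SAP rule would then need to be aligned with it.

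**Conclusion.** The point holds as a modest improvement. Section 3.3 confines strain sepsis to two separate analyses, and section 5.3 provides no usable ratio if an arm has no cases. With zero cases, a combined exact interval would have an upper limit of 0.53 per 1,000, beside 0.78 for preterm and 1.64 for term SGA infants. The gain is about a third against the preterm limit and large only against the term SGA limit.

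These figures assume that enrolment reaches the stated targets, that each infant counts once, and that few or no cases occur. A reader might infer a flaw in the primary results or in how safety data are collected. The document supports neither: the point concerns only how one secondary safety outcome is summarised.

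**What to change.** In section 3.3, keep the separate presentations and add:

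> For sepsis due to *B. infantis* or *L. rhamnosus*, a combined analysis of all randomised infants, stratified by infant status and site, will also be reported beside the group-specific results, with exact two-sided 95% confidence intervals for the risk among intervention infants in each group and combined.

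Section 5.2 should state that risk here means the proportion of infants with at least one such episode. A footnote to the table should say that the combined figure is an average over the enrolled mix. A combined summary of serious adverse events is optional.

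The cost is a few lines in the SAP and one more table. No new data are needed and the primary analyses do not change. The wording should be settled before unblinding.

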5.1. Primary outcome definitions

- Mortality from enrolment to 6 months of age among preterm infants: the proportion of infants who die from any cause from enrolment to 6 months of age.
- Underweight-free survival from enrolment to 6 months of age among term SGA infants: the proportion of infants with WAZ ≥ -2 at 6 months of age and who have not died.

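### The secondary per-protocol sets require all 28 days of product, so infants who die before dosing ends are left out of the per-protocol mortality analysis

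*SAP*

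**What the plan says.** SAP section 3.3 makes the analysis of all randomised infants primary and adds per-protocol analyses as secondary. The two PP sets are "Randomised preterm infants who receive all 28 days of intervention/control (Preterm PP): for primary outcome 1 and all secondary outcomes" and "Randomised term SGA infants who receive all 28 days of intervention/control (Term SGA PP): for primary outcome 2 and all secondary outcomes". Within them, infants are to be analysed "with participants analysed according to the treatment received rather than the treatment to which they were randomised" if the two differ.

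Section 2.2 sets dosing "once daily for a period of 28 days". Section 5.1 defines the preterm primary outcome as "the proportion of infants who die from any cause from enrolment to 6 months of age" and the term SGA primary outcome as "the proportion of infants with WAZ ≥ -2 at 6 months of age and who have not died". Section 2.6 evaluates the mortality outcomes and the main morbidity outcomes at hospital discharge, age one month and age six months.

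The SAP makes no exception for death during dosing. It has no day-28 starting point for PP outcomes, no adherence rule based on doses due, and no method for adherence that varies over time. Section 4.1 counts infants who received all 28 doses in the flow diagram, which supports the literal reading of the PP rule.

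**The concern.** An infant has to survive the dosing period to receive 28 daily doses, yet the outcome clock starts at enrolment. Deaths during dosing are therefore removed from both arms by the definition of the population. What remains compares later mortality among survivors, while being labelled mortality from enrolment.

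Three consequences follow.

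- The PP risk ratio cannot show benefit or harm that appears as deaths during supplementation.
- The discharge and 1-month outcomes lose most of their meaning: in-hospital deaths before dosing ends are dropped, and 1-month mortality is left with almost nothing to count.
- PP analyses of SAEs, sepsis and necrotising enterocolitis lose every infant who died before completing dosing.

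Readers commonly set a PP result beside the ITT result as a check on it. Here the two could disagree only because of when deaths happened.

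**Working it through.** **Inputs.** From SAP section 2.3: preterm mortality of 10% against 8%, 90% power, 5% significance level, 8,602 infants with data; term SGA underweight-free survival of 23% against 27.6%, 3,750 infants with data. From section 3.1: two-sided tests. From section 2.2: 1:1 allocation.

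**Reproducing the plan's figures.** For two proportions with pooled variance under the null and no continuity correction,

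n per arm = [1.960·√(2·p̄·(1−p̄)) + 1.282·√(p₁(1−p₁) + p₂(1−p₂))]² / (p₁−p₂)².

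With 0.10 and 0.08 (p̄ = 0.09) this gives 4,301 per arm, or 8,602. With 0.23 and 0.276 it gives 1,875 per arm, or 3,750. Both match, so the point is not about the sample size. The expected deaths are 4,301 × 0.10 ≈ 430 and 4,301 × 0.08 ≈ 344, in total 774.

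**Assumptions, not in the SAP.** A share s of control deaths falls during dosing, with s from 30% to 70%. Every infant who survives dosing completes all 28 days. The ITT risk ratio is 0.80.

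**Formula.** In each arm, PP risk = (risk of death after dosing) / (1 − risk of death during dosing), with both risks per randomised infant. In the control arm this is 0.10(1−s) / (1−0.10s).

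| s | Control deaths removed | Control PP risk | PP RR, same effect in both periods (power) | PP RR, all benefit during dosing | PP RR, all benefit after dosing |
|---|---|---|---|---|---|
| 30% | 129 | 7.2% | 0.795 (79%) | 0.980 | 0.714 |
| 50% | 215 | 5.3% | 0.792 (65%) | 0.979 | 0.600 |
| 70% | 301 | 3.2% | 0.788 (45%) | 0.979 | 0.333 |

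**One row in full (s = 50%).** The control risk is 0.05 during dosing and 0.05 after it, so the PP risk is 0.05/0.95 = 5.26%.

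- Same effect in both periods: the intervention risks are 0.04 and 0.04, so the PP risk is 0.04/0.96 = 4.17% and the RR is 0.792. The sets hold 4,301 × 0.95 ≈ 4,086 and 4,301 × 0.96 ≈ 4,129 infants, and power is 65%.
- All benefit during dosing: 0.03 during and 0.05 after. The PP risk is 0.05/0.97 = 5.15% and the RR is 0.979.
- All benefit after dosing: 0.05 during and 0.03 after. The PP risk is 0.03/0.95 = 3.16% and the RR is 0.600.

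**Term SGA.** Deaths are failures of underweight-free survival, so removing early deaths shrinks the denominator. Assume dosing-period mortality of 2-4% in control and a mortality RR of 0.80.

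- At 2%: 0.23/0.98 = 23.5% and 0.276/0.984 = 28.0%, RR 1.195.
- At 4%: 0.23/0.96 = 24.0% and 0.276/0.968 = 28.5%, RR 1.190.

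The design value is 1.20.

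**The 1-month outcome.** Dosing runs from enrolment, while the outcome is set by age. A PP infant can be counted as dead at 1 month only if the death falls between the last dose and age one month.

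**The case against.** The strongest reply is that little depends on these analyses. They are secondary. The SAP names all randomised infants as the analysis population for each primary outcome, and its effect tables (Tables 3 to 7) are all headed as ITT. The interim rule in section 2.4 does not mention a PP set, and the sample size was not set for one. All of this stands. A reader might infer that the trial's main mortality result is biased; the SAP does not support that, because ITT keeps every death.

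Other strong readings also go further than the text.

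- *PP mortality at 1 month is exactly zero.* The SAP gives neither age at enrolment nor one month in days, so a few deaths after the last dose could still count. Near zero is what can be said.
- *Infants taken off product because of necrotising enterocolitis or sepsis are removed.* The SAP has no rule for stopping doses, so this cannot be asserted from it.
- *The PP analysis always dilutes the effect.* It can also exaggerate it, as the last column of the table shows.
- *An early benefit gives a PP risk ratio of exactly 1.00.* That requires equal later risk among survivors. With equal later deaths per randomised infant it is about 0.98.

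The power figures are illustrative, since they rest on an assumed timing of deaths and full completion among survivors. Analysis by product received is a separate departure from randomisation and is not evidence for the survival problem.

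What the reply does not remove is that the PP rule, followed as written, selects infants by the outcome it is then used to compare.

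**Conclusion.** The point holds for the secondary PP analyses and should be fixed; it does not threaten the primary analysis. For the same true ITT risk ratio of 0.80, the preterm PP risk ratio could lie anywhere from about 0.33 to 0.98, depending only on when the effect occurs. With a constant effect it stays at 0.79-0.80, but power falls from 90% to between about 79% and 45%. These ranges rest on 30-70% of control deaths falling during dosing and on all survivors completing it. The SAP supplies neither figure, so the size and direction of the bias cannot be settled from it.

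A reader might infer equal damage to the term SGA outcome because the same rule applies. The figures do not support that: the risk ratio moves only from 1.20 to about 1.19 under the assumed 2-4% dosing-period mortality.

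**What to change.** Amend section 3.3 in one of two ways, before any unblinding so that the change cannot look driven by the data.

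(a) Define PP by adherence to the doses due while the infant is alive and in follow-up, up to day 28, and analyse in the randomised arm. State expressly that doses missed in the illness leading to death do not exclude the infant; without that rule, membership would still depend on dying.

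(b) Keep completion of 28 days only as a day-28 landmark analysis of later events, labelled as conditional on survival, and drop it for the discharge and 1-month outcomes.

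The cost is SAP wording and one derived variable; section 4.3 already summarises receipt of each dose from day 1 to day 28. Neither option is free of assumptions. Under (a), an infant who dies on the first day counts as adherent, and attributing missed doses to a final illness needs a rule set in advance. Under (b), the analysis says nothing about the dosing period. Either way the PP estimate still rests on assumptions about adherence and should be reported as such.
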